1.3.2. Benefit Assessment

In subjects with T2DM, the clinical data showed that once weekly albiglutide treatment (both the 30 mg and 50 mg doses), in an easy-to-use pen device, resulted in clinically relevant lowering of HbA1c when given as monotherapy and in combination with

metformin, sulphonylureas, thiazolidinediones (TZD) and basal insulin (reference: IB Section 5.5). Furthermore, the durability of the effect on these glycaemic parameters was shown over a study period of 3 years. In the two Phase III studies that compared albiglutide to insulin treatment (i.e., insulin glargine in one study and insulin lispro in the other), albiglutide therapy was associated with approximately 1.5-to 2-fold less symptomatic hypoglycaemia and with weight loss rather than weight gain (treatment difference of 1.5-2.6 kg).

In this current study in NOT1DM, where albiglutide treatment will be added to a regimen of basal/meal-time insulin therapy, the subject is expected to achieve similar glycaemic control to the group taking insulin alone, but with a reduced total daily insulin dose, reduced glycaemic variability (hypoglycaemia and hyperglycaemia) and reduced weight gain.

The anticipated benefit of albiglutide in NOT1DM is to delay or prevent deterioration of pancreatic β -cell function. Residual β -cell function is important for patients because the clinical course of their diabetes tends to be more stable, easier to manage, with less hyperglycaemia (including less DKA), less hypoglycaemia (including fewer serious episodes), a lower exogenous insulin requirement [[Ostman, 2000](#); [Madsbad, 1979](#); [Home, 2003](#)] and ultimately in the very long-term, fewer vascular complications [[Steffes, 2003](#); [DCCT, 1998](#)], the latter will not be evaluated in this year-long study.

Finally, as a result of participating in a clinical trial, each subject will receive more contact with the study site, have diet and exercise advice reinforced at each visit, and more enhanced supervision of their diabetes than would be performed as part of their usual standard of care.

1.3.3. Overall Benefit:Risk Conclusion

Taking into account the measures taken to minimise risk to subjects participating in this study, the potential risks identified in association with albiglutide are justified by the anticipated benefits that may be afforded to patients with NOT1DM.

2. OBJECTIVE(S)

2.1. Primary Objective

- Determine the effect of albiglutide therapy versus placebo on endogenous insulin secretion over 52 weeks when added to standard of care in subjects with new onset type 1 diabetes mellitus (NOT1DM).

2.2. Secondary Objectives

- To assess the effect of albiglutide versus placebo on plasma glucagon concentration during a mixed meal tolerance test (MMTT)
- Determine the percentage of subjects meeting the definition of a responder (defined as having $HbA_{1c} \leq 7.0\%$ and mean daily insulin use < 0.5 units/kg/day) and the

percentage of subjects achieving partial remission status (i.e., defined as subjects with Insulin Dose Adjusted A1c (IDAA1C) \leq 9.0)

- To assess glycaemic control in both treatment groups as measured by HbA1c
- Determine differences in total daily insulin dose between treatment groups
- Determine any differences in significant hypoglycaemia (i.e., events with plasma glucose $<$ 3.9 mmol/L and/or requiring third party intervention) between treatment groups
- Compare glycaemic variability between treatment groups, as measured by 72-hour continuous glucose monitoring (CGM) and 7 point glucose profile
- Determine the effect of albiglutide on body weight
- Assess the safety and tolerability of albiglutide in subjects with NOT1DM
- To evaluate the albiglutide PK profile in subjects with NOT1DM

2.3. Exploratory Objectives

- Assess the effect of albiglutide on T1DM-associated auto-antibodies (antibody to glutamic acid decarboxylase (anti-GAD) antibody to protein tyrosine phosphatase-like protein (anti-IA-2) and insulin autoantibody (IAA))
- Explore whether urinary C-peptide could be used in future phase III studies as an alternative to plasma C-peptide AUC from mixed meal testing as a measure of endogenous insulin secretion
- To evaluate the PK and PD (PK/PD) relationship between plasma albiglutide concentration and measures of glycaemic control (e.g., C-peptide, insulin use, HbA1c, etc) as data permit.
- To explore the PK/PD relationship between albiglutide and other potential efficacy, tolerability (e.g., nausea and vomiting), and safety endpoints as data permit
- Assess the effect of albiglutide on biomarkers associated with autoimmune pathology over 52 weeks in subjects with NOT1DM.
- Assess the effect of albiglutide on diabetes-related quality of life as measured by the Audit of Diabetes Dependent Quality of Life questionnaire (ADDQoL).
- Assess the effect of albiglutide on β -cell function in the context of the prevailing glucose response to the MMTT

3. INVESTIGATIONAL PLAN

3.1. Study Design

This Phase II, randomised, double-blind, parallel group, placebo controlled, multicentre study of 52 weeks treatment duration will evaluate the efficacy, safety and tolerability of weekly albiglutide versus placebo when added to insulin therapy in subjects with

NOT1DM and residual insulin production. The primary endpoint is mean change from baseline in mixed meal stimulated 2 hour plasma C-peptide AUC at Week 52.

Subjects within 8 weeks of diagnosis, who are receiving insulin treatment or have received insulin at some time between the date of diagnosis and the first dose of study drug, with one or more positive T1DM associated auto-antibodies, and a stimulated peak C-peptide > 0.2 nmol/L, signifying clinically relevant residual C-peptide production (as a measure of β cell function), will be eligible to enter the study.

[figure not shown]
After screening, approximately 68 eligible subjects will be randomised in a 3:1 ratio such that:

- 51 subjects receive albiglutide 30 mg once weekly (with increase to 50 mg once weekly at Week 6 if the 30-mg weekly dose is tolerated) added-on to insulin therapy
- 17 subjects receive placebo once weekly added-on to insulin therapy

During the study, subjects will perform self monitoring of plasma glucose at least 4 times daily and adjust their basal and meal-time insulin requirements according to protocol-defined algorithm/guidance (See Section 5.1.2).

The total duration of a subject's participation will be approximately 72 weeks (up to 8 weeks of Screening, 52 weeks of treatment and 12 weeks of Post-treatment Follow-up) (Figure 1). Subjects will have 12 study centre visits and at least 14 telephone calls.

Figure 1 Study Schematic for GLP110933

Potential events of pancreatitis will be adjudicated by an independent pancreatitis adjudication committee (PAC).

Subject completion is defined as completion of all periods of the study up to and including the follow-up period.

There will be no compassionate use of study medication once a subject completes or withdraws early from the study.

Protocol waivers or exemptions are not allowed with the exception of immediate safety concerns. Therefore, adherence to the study design requirements, including those specified in the Time and Events Table ([Table 3](#)), are essential and required for study conduct.

Supplementary study conduct information not mandated to be present in this protocol is provided in the accompanying Study Procedures Manual (SPM). The SPM will provide the site personnel with administrative and detailed technical information that does not impact subject safety.

3.2. Discussion of Design

The design of this study and chosen endpoints i.e., randomised, double-blind, placebo-controlled with primary endpoint assessment after one year in T1DM subjects with documented residual β -cell function, are in line with guidance provided by both the EMA and FDA for the development of drugs aimed at preservation of β cell function in T1DM [FDA, 2008; EMA, 2012]. Currently there are no approved treatments for preservation of β -cell function in T1DM subjects.

Endogenous insulin secretion, as a key measure of β -cell function, is being assessed in this study by using the plasma C-peptide AUC following a mixed meal. When pancreatic β cells produce insulin, they also produce C-peptide in equimolar amounts. C-peptide has a longer half life than insulin and unlike insulin, experiences little first pass clearance by the liver. C-peptide connects the two components of pro-insulin and is released when the pro-hormone is activated [Gianani, 2005; Palmer, 2004]. Measurement of C-peptide under standardised conditions in response to a mixed meal challenge provides a sensitive, well accepted, and clinically validated assessment of endogenous insulin secretion and β cell function [Palmer, 2004].

As indicated in the EU guidelines for developing drugs that preserve β -cell function, pharmacological intervention will likely need to be initiated as soon as possible after manifestation of the disease to have a chance of showing a meaningful benefit (since greater than 80% of β -cell function may have been lost by the time of diagnosis and it continues to decline after diagnosis). Accordingly, in this study, subjects are to commence treatment with study drug within 8 weeks of diagnosis. This time interval was selected as a balance between maximising the potential to preserve the remaining β -cell function (by treating as early as possible after diagnosis) and feasibility (allowing time for subjects to consent to the study and to perform the screening assessments).

A stimulated C-peptide >0.2 nmol/L was selected as the cut-off for study entry as this level of C-peptide is the most widely used by researchers to represent clinically meaningful RBCF based on data from the DCCT [Diabetes Control and Complications Trial Research Group], 1998. The clinical importance of this cut-off was initially determined during the feasibility phase of the DCCT, in which metabolic parameters including fasting and post-prandial glucose levels, HbA1c, and daily insulin dosage, were compared among patients with stimulated C-peptide levels in 4 categories: >0.2 nmol/L; $>0.1 - 0.2$ nmol/L; $>0.05 - 0.1$ nmol/L; and ≤ 0.05 nmol/L [DCCT, 1987]. The group with a C-peptide >0.2 nmol/L had statistically significantly lower values for all of these parameters (indicating better metabolic control) than the other 3 groups. In the larger DCCT study, patients with stimulated C-peptide >0.2 nmol/L at study entry had a reduced risk of retinopathy (or progression of retinopathy), microalbuminuria, and hypoglycaemia (including severe hypoglycaemia), and a lower HbA1c than patients with C-peptide <0.2 nmol/L [DCCT, 1998; DCCT, 1997].

The control arm of this study will be placebo. To allow for a 3:1 randomisation ratio (albiglutide: placebo), historical data from the DEFEND-1 study [GlaxoSmithKline Document Number, 2011N125757_00] has been used as prior knowledge. In DEFEND-1, 53 subjects with similar inclusion/exclusion criteria were randomised to the placebo

group. Stimulated C-peptide data from a MMTT were collected at the same 52-week primary endpoint and therefore provide important safety and efficacy information for the placebo subjects. With this historical knowledge of placebo subjects, a Bayesian analysis method can be used which means fewer placebo subjects are required for this current study.

Subjects in both arms of the study will be on background insulin therapy (or will have required insulin for more than 7 days since diagnosis) - the standard of care for T1DM. Insulin may be titrated up or down to maintain glycaemic control throughout the study according to treat-to-glycaemic target protocol-defined insulin titration algorithms. Observing the drug effect versus placebo on top of standard of care background therapy will allow a better understanding of the efficacy, safety and tolerability profile of albiglutide in NOT1DM.

Data from 8 Phase III studies in subjects with T2DM (GLP108486, GLP112753, GLP112754, GLP112755, GLP112756, GLP112757, GLP114179 and GLP114130) have confirmed that both albiglutide 30 mg and 50 mg demonstrated robust efficacy and were generally well-tolerated in this patient population. Although a 30 mg dose of albiglutide was effective at controlling glycaemia for at least 2 years in many T2DM subjects, an increase in dose to 50-mg weekly offered additional benefit without significant safety issues (See IB for further details). The albiglutide dose in this study will start at 30-mg weekly and be increased to 50-mg weekly at Week 6 if the patient is able to tolerate the 30 mg weekly dose. Week 6 was chosen as the point for up-titration as it provides a sufficient length of time for subjects with NOT1DM to have their insulin doses stabilise and achieve steady-state exposures with 30 mg albiglutide (achieved following 4 to 5 weeks of once-weekly administration).

Forced up-titration will allow a more homogenous evaluation of albiglutide at its highest approved dose (for the treatment of T2DM) without the confounding effects of dose and time. Hyperglucagonaemia can also occur in NOT1DM. Increasing the dose of albiglutide to 50 mg at Week 6 offers the opportunity to further reduce hyperglucagonaemia, hence minimising β -cell stress. The higher dose will therefore maximise the potential benefit of albiglutide treatment on endogenous insulin secretion in subjects with NOT1DM.

Subjects experiencing GI intolerance on the 50 mg dose may decrease back to the 30 mg dose following discussion between the investigator and the medical monitor. This is included in the study design as it is important to keep subjects on albiglutide as long as possible to maximise the chance of being able to ascertain any therapeutic effect on β cell function.

Glucose variability will be assessed by 2 methods - the 7 point glucose profile and continuous glucose monitoring (CGM). Whilst the 7 point glucose profile is the established method for assessing glucose variability in clinical practice and in studies, CGM is gaining popularity and is recommended for use in diabetes trials by the EMA as it provides more detailed information on variability (glucose is sampled every 5 mins for 72 hours compared to the 7 point profile which only assesses glucose at 7 fixed time-points over a 24 hour period). However, it is not yet fully validated, it can be subject to

technical failures, measures glucose in tissue fluid rather than plasma, must be calibrated with fingerstick blood glucose values several times a day and is more valuable in looking for trends than absolute values. Hence both measures are included in the protocol.

Subjects will return for a follow-up visit at Week 64 (12 weeks after the end of the 52-week treatment period). The purpose of this follow-up is to determine if the effect of albiglutide treatment on endogenous insulin secretion is still apparent 12 weeks after stopping treatment (thus suggesting that albiglutide is disease modifying). Subjects will continue to follow the insulin titration algorithm described in Section 5.1.2 until completion of the Week 64 follow-up visit, to ensure equivalent glycaemic control is maintained in the 2 treatment arms throughout the follow-up period.

4. SUBJECT SELECTION AND WITHDRAWAL CRITERIA

4.1. Number of Subjects

Approximately 68 subjects will be randomised to achieve 60 evaluable subjects. Note: if the withdrawal rate from the study is larger than expected, consideration will be given to replacing subjects who withdraw from the study.

4.2. Inclusion Criteria

Specific information regarding warnings, precautions, contraindications, adverse events, and other pertinent information on the GSK investigational product or other study treatment that may impact subject eligibility is provided in the IB/IB supplement(s), product label, add other pertinent documents.

Deviations from inclusion criteria are not allowed because they can potentially jeopardise the scientific integrity of the study, regulatory acceptability or subject safety. Therefore, adherence to the criteria as specified in the protocol is essential.

Subjects eligible for enrolment in the study must meet all of the following criteria:

1. Male or female, aged 18 to 30 years, inclusive, with a diagnosis of T1DM with an interval of 28-56 days between the initial diagnosis and the first dose of study drug. Documentation of the diagnosis of T1DM (and not just insulin deficiency), including the date of diagnosis, must be obtained from the diagnosing physician.
2. Currently requires insulin for T1DM treatment, or has required insulin therapy for T1DM (for ≥ 7 days) between the date of diagnosis and the first dose of study drug
Note: subjects currently taking twice daily commercially available pre-mixed insulin will not be eligible.
3. Positive for at least one of the following autoantibodies typically associated with T1DM: antibody to glutamic acid decarboxylase (anti-GAD) antibody to protein tyrosine phosphatase-like protein (anti-IA-2) or an insulin autoantibody (IAA).

Please note: A subject who is positive for IAA and negative for the other autoantibodies will not be eligible if the subject has been using insulin for a total of ≥ 7 days.

4. Evidence of residual functioning pancreatic β -cells as measured by a peak stimulated C-peptide level > 0.20 nmol/L during the Screening MMTT when plasma glucose level is > 3.9 mmol/L (70 mg/dL) and ≤ 11.1 mmol/L (200 mg/dL).

Note: the Screening MMTT should not be performed within one week of resolution of a DKA event.

5. Body mass index ≤ 32.0 kg/m².
6. Female subjects of childbearing potential (i.e., not surgically sterile and/or not postmenopausal) must be practicing adequate contraception (i.e., meeting one of the criteria defined below) from at least 14 days prior to the first dose of randomised study medication until the 12-week post-treatment Follow-up visit
 - Abstinence from penile-vaginal intercourse, when this is the female's preferred and usual lifestyle
 - Oral Contraceptive, either combined or progestogen alone
 - Injectable progestogen
 - Implants of etonogestrel or levonorgestrel
 - Estrogenic vaginal ring
 - Percutaneous contraceptive patches
 - Intrauterine device or intrauterine system that has a failure rate of less than 1% per year when used consistently and correctly as stated in the product label
 - Male partner sterilization prior to the **female subject's entry** into the study, and this male is the sole partner for that subject. The information on the male sterility can come from the site personnel's review of subject's medical records; medical examination of the subject and/or semen analysis; or interview with the subject on his medical history.
 - Male condom **combined with a female** diaphragm, either with or without a vaginal spermicide. [**UK only**: this method of contraception is acceptable only if used with a vaginal spermicide].
7. Able and willing to provide written informed consent and to comply with all study procedures.

4.3. Exclusion Criteria

Deviations from exclusion criteria are not allowed because they can potentially jeopardise the scientific integrity of the study, regulatory acceptability or subject safety. Therefore, adherence to the criteria as specified in the protocol is essential.

Subjects meeting any of the following criteria must not be enrolled in the study:

1. Severe gastroparesis i.e., requiring therapy within 6 months prior to Screening
2. History of acute or chronic pancreatitis, or considered clinically at significant risk of developing pancreatitis, during the course of the study (e.g. due to symptomatic gallstones, excess alcohol use).
3. History of significant gastrointestinal surgery that in the opinion of the investigator is likely to significantly affect upper gastrointestinal or pancreatic function (e.g. gastric bypass and banding, antrectomy, Roux-en-Y bypass, gastric vagotomy, small bowel resection, or surgeries thought to significantly affect upper gastrointestinal function)
4. Personal history or family history of thyroid medullary carcinoma or multiple endocrine neoplasia type 2 (MEN2)
5. History of cancer that has not been in full remission for at least 3 years before Screening. (A history of squamous cell or basal cell carcinoma of the skin, or treated cervical intraepithelial neoplasia I or cervical intraepithelial neoplasia II is allowed)
6. Fasting triglyceride level >750 mg/dL at Screening. Subjects may be re-tested once during screening, and if the value no longer meets the exclusion criterion, the subject can be randomly assigned to treatment
7. Estimated Glomerular Filtration Rate (eGFR) ≤ 30 mL/min/1.73 m² (calculated using the Modification of Diet in Renal Disease (MDRD) formula)
8. Haemoglobinopathy that may affect proper interpretation of HbA_{1c}
9. Alanine aminotransferase (ALT) $>2.5 \times$ upper limit of normal (ULN) and bilirubin $>1.5 \times$ ULN (isolated bilirubin $>1.5 \times$ ULN is acceptable if bilirubin is fractionated and direct bilirubin $<35\%$)
10. Unstable liver disease (as defined by the presence of ascites, encephalopathy, coagulopathy, hypoalbuminemia, oesophageal or gastric varices or persistent jaundice), cirrhosis, known biliary abnormalities (with the exception of Gilbert's syndrome or asymptomatic gallstones). [Chronic stable hepatitis B and C are acceptable if subject otherwise meets entry criteria and are not on active antiviral treatment (e.g., presence of hepatitis B surface antigen or positive hepatitis C test result within 3 months of screening)]
11. Any clinically significant co-morbidity or abnormality (including psychiatric disorder, any other autoimmune endocrinopathy e.g., primary autoimmune hypothyroidism, hypoadrenalism, coeliac disease etc) that in the opinion of the Investigator, may pose additional risk in administering study medication or trial participation
12. Female subject is pregnant (confirmed by laboratory testing) or lactating
13. Known allergy to any GLP-1 analogue, insulin, or excipients of albiglutide
14. Treatment with any oral anti-diabetic medication within the prior 30 days or 5 half-lives of that medication, whichever is longer.
15. Use of immunosuppressants, intravenous immunoglobulin, oral or systemically injected glucocorticoids within the 3 months before randomisation or high likelihood of a requirement for prolonged treatment (>1 week) in the year following randomisation. However, short courses of oral steroids (single dose or multiple doses

for up to 7 days) may be permitted provided these cases are discussed with the medical monitor. Inhaled, intra-articular, and small quantities of non-potent topical corticosteroids are allowed

16. Receipt of any investigational drug within the 30 days or 5 half-lives, whichever is longer, before Screening, a history of receipt of an investigational anti-diabetic drug within the 3 months before randomisation, or receipt of albiglutide in previous studies

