Thyroid C-cell tumours [potential risk]	This potential risk arises from non-clinical rodent studies where GLP-1R agonists have been associated with increases in serum calcitonin, thyroid C-cell focal hyperplasia, and C-cell tumours. The relevance of these observations to man is uncertain. In phase III studies of up to 3 years duration, albiglutide was not associated with clinically relevant increases in serum calcitonin (Refer to Section 5.4.5.3 and Section 6 of the IB)..	Subjects with a personal or family history of MTC or Multiple Endocrine Neoplasia syndrome type 2 are excluded (see Section 4). Risk communication via Guidance For Investigators (IB Section 6) and informed consent form for subject
Other malignant neoplasms (e.g., pancreatic cancer and malignancy when used with insulin) [potential risk]	Theoretical concern pancreatic cancer associated with GLP-1 based therapies (DPPIV-inhibitors and GLP-1R agonists) under evaluation by regulatory authorities (Egan; 2014), and has thus far concluded that a causal relationship cannot be established currently but they will continue to investigate as more data becomes available. Theoretical concern raised by EU regulatory authorities based on the biological plausibility of a tumour-promoting effect when a GLP-1R agonist is combined with insulin	No mitigation strategy

Identified/Potential/Other Risk of Clinical Significance	Data / Rationale for Risk	Mitigation Strategy
Hepatotoxicity [Potential risk]	One subject in the Phase III clinical programme developed probable drug induced liver injury with an asymptomatic elevation in ALT and total bilirubin although the cases had some atypical features and complicating factors. (Refer to Section 5.4.5.7 of the IB).	Specific eligibility and withdrawal criteria (See Section 4).
Patient population with severe renal Impairment (eGFR < 30 mL/min/1.73 m ²) [Other risk]	Experience of albiglutide in T2DM patients with severe renal impairment is very limited Patients with severe renal impairment receiving albiglutide experienced a higher frequency of diarrhoea, nausea, and vomiting compared to patients with mild/moderate renal impairment (Refer to Section 5.4.6 and Section 6 of the IB).	Specific eligibility criterion (See Section 4). Risk communication via Guidance For Investigators (IB Section 6) and informed consent form for subject

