4.4. Withdrawal Criteria

Any subject who discontinues randomised study medication for any reason, after receiving at least one dose, will be asked to remain in the study and attend selected visits (see below) for collection of long-term efficacy and safety data (i.e., withdrawal of study drug does not require withdrawal from the study).

Every effort should be made to keep subjects in the study. The reasons for subjects discontinuing study medication and/or not completing the study will be recorded.

Consideration will be given to replacing subjects who withdraw from the study.

Reasons for study drug discontinuation

- These AEs **will** require study drug withdrawal:
 - Elevation of liver function test results according to the criteria in Section [6.4.9](#),
 - Severe allergic/hypersensitivity reactions that are considered by the investigator to be attributable to randomised study medication or without a likely alternative etiology (see Section [6.4.14](#))
 - Confirmed acute or chronic pancreatitis (see Section [6.4.15](#))
 - Confirmed medullary thyroid cancer
- AE, which, in the opinion of the investigator or subject precludes continuation of dosing
- Loss to follow-up (the investigator must make every effort to contact subjects lost to follow-up)
- Study closed/terminated or Investigator site closed
- Pregnancy or intention of becoming pregnant
- Protocol deviation (the investigator should discuss the protocol deviation with the sponsor before withdrawing study drug)
- Subject decision (reason to be documented in the electronic case report form (eCRF), if specified by the subject)
- Investigator discretion

Subjects who discontinue study medication will be asked to continue to attend the study visits where a MMTT is performed through to Week 64 (i.e., Week 16, Week 28, Week 52 and Week 64). During these visits where a MMTT will be performed, HbA1c, weight, AEs, hypoglycaemia and insulin usage will also be assessed. Subjects will also be asked to continue completing diaries for insulin usage and hypoglycaemia events. Additionally, the insulin titration algorithm/guidelines should continue to be followed through to Week 64.

While participating in the study, subjects should not receive any additional antidiabetic medication (except insulin) or investigational agents until after the Week 64 visit.

Reasons for withdrawal from the study

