6.4.9. Liver chemistry stopping and follow up criteria

Liver chemistry stopping and follow up criteria have been designed to assure subject safety and evaluate liver event etiology (in alignment with the FDA premarketing clinical liver safety guidance).

liver chemistry stopping criteria 1-5 are defined below and are presented in a figure in Appendix 2 :

1. ALT \geq 3xULN and bilirubin \geq 2xULN (>35% direct bilirubin) (or ALT \geq 3xULN and INR>1.5, if INR measured)

NOTE: if serum bilirubin fractionation is not immediately available, withdraw study drug for that subject if ALT \geq 3xULN and bilirubin \geq 2xULN. Serum bilirubin fractionation should be performed if testing is available. If testing is unavailable, **record presence of detectable urinary bilirubin on dipstick**, indicating direct bilirubin elevations and suggesting liver injury.

2. ALT \geq 8xULN.
3. ALT \geq 5xULN but <8 xULN persists for \geq 2 weeks

4. ALT \geq 3xULN if associated with symptoms (new or worsening) believed to be related to hepatitis (such as fatigue, nausea, vomiting, right upper quadrant pain or tenderness, or jaundice) or hypersensitivity (such as fever, rash or eosinophilia).
5. ALT \geq 5xULN but $<$ 8 xULN and cannot be monitored weekly for \geq 2 weeks

When any of the liver chemistry stopping criteria 1-5 is met, do the following:

- **Immediately** withdraw investigational product for that subject
- Report the event to GSK **within 24 hours** of learning its occurrence
- Complete the liver event CRF and SAE data collection tool if the event also meets the criteria for an SAE. All events of ALT \geq 3xULN **and** bilirubin \geq 2xULN ($>$ 35% direct) (or ALT \geq 3xULN **and** INR $>$ 1.5, if INR measured); INR measurement is not required and the threshold value stated will not apply to patients receiving anticoagulants), termed 'Hy's Law', **must be reported as an SAE (excluding studies of hepatic impairment or cirrhosis).**

NOTE: if serum bilirubin fractionation is not immediately available, withdraw study drug for that subject if ALT \geq 3xULN **and** bilirubin \geq 2xULN. Serum bilirubin fractionation should be performed if testing is available. If testing is unavailable, **record presence of detectable urinary bilirubin on dipstick**, indicating direct bilirubin elevations and suggesting liver injury.

- Complete the liver imaging and/or liver biopsy CRFs if these tests are performed

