- Perform liver event follow up assessments, and monitor the subject until liver chemistries resolve, stabilise, or return to baseline values as described below.
- The subject may remain in the study as described in Section 4.4, however, investigational product must not be restarted

In addition, for criterion 1:

- Make every reasonable attempt to have subjects return to clinic **within 24 hours** for repeat liver chemistries, liver event follow up assessments (see below), and close monitoring
- A specialist or hepatology consultation is recommended
- Monitor subjects twice weekly until liver chemistries (ALT, AST, alkaline phosphatase, bilirubin) resolve, stabilise or return to within baseline values

For criteria 2, 3, 4 and 5:

- Make every reasonable attempt to have subjects return to clinic **within 24-72 hrs** for repeat liver chemistries and liver event follow up assessments (see below)
- Monitor subjects weekly until liver chemistries (ALT, AST, alkaline phosphatase, bilirubin) resolve, stabilise or return to within baseline values; criterion 5 subjects should be monitored as frequently as possible.

Subjects with ALT $\geq 5xULN$ and $< 8xULN$ which exhibit a decrease to ALT $\times \geq 3xULN$, but $< 5xULN$ and bilirubin $< 2xULN$ without hepatitis symptoms or rash, and who can be monitored weekly for 4 weeks:

- Notify the GSK medical monitor within 24 hours of learning of the abnormality to discuss subject safety
- Can continue investigational product
- Must return weekly for repeat liver chemistries (ALT, AST, alkaline phosphatase, bilirubin) until they resolve, stabilise or return to within baseline
- If at any time these subjects meet the liver chemistry stopping criteria, proceed as described above
- If, after 4 weeks of monitoring, ALT $< 3xULN$ and bilirubin $< 2xULN$, monitor subjects twice monthly until liver chemistries normalise or return to within baseline values.

For criteria 1-5, make every attempt to carry out the **liver event follow up assessments** described below:

- Viral hepatitis serology including:
 - Hepatitis A IgM antibody;
 - Hepatitis B surface antigen and Hepatitis B Core Antibody (IgM);
 - Hepatitis C RNA;
 - Cytomegalovirus IgM antibody;
 - Epstein-Barr viral capsid antigen IgM antibody (or if unavailable, obtain heterophile antibody or monospot testing);
 - Hepatitis E IgM antibody

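### Exclusion criterion 9 joins its ALT and bilirubin limits with *and*, so its isolated-bilirubin exception does nothing and isolated ALT has no numeric entry limit

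*Protocol*

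**What the plan says.** Protocol 4.3 bars anyone who meets any one of its exclusion criteria and permits no deviations. Criterion 9 sets ALT above 2.5 times the "upper limit of normal (ULN) and bilirubin" above 1.5×ULN. Its parenthesis says that isolated bilirubin above 1.5×ULN "is acceptable if bilirubin is fractionated and direct bilirubin" is below 35%.

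Two neighbouring criteria bear on the liver:

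- Criterion 10 excludes overt liver disease on clinical grounds and states "Chronic stable hepatitis B and C are acceptable if subject otherwise meets entry criteria".
- Criterion 11 excludes a clinically significant co-morbidity or abnormality "that in the opinion of the Investigator, may pose additional risk in administering study medication or trial participation".

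The hepatotoxicity row of the risk table (Protocol 1.3.1) gives its mitigation as "Specific eligibility and withdrawal criteria (See Section 4").

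On treatment, Protocol 6.4.9 sets ALT stopping criteria as multiples of ULN. When one is met, sites must immediately "withdraw investigational product for that subject". It adds: "The subject may remain in the study as described in Section 4.4, however, investigational product must not be restarted". Protocol 4.4 confirms that "withdrawal of study drug does not require withdrawal from the study".

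**The concern.** An exception needs something to except. If both elevations are required for exclusion, raised bilirubin alone never excludes anyone, and a conditional acceptance of it is redundant. The parenthesis makes sense only if each limit applies separately, which suggests that *or* was intended.

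The practical gap is isolated ALT. As written, ALT at any level passes criterion 9 if bilirubin is at or below 1.5×ULN. Such a subject could start study drug at or near an on-treatment stopping threshold, lose the drug permanently, and make any later drug-related liver signal harder to read. The risk table relies partly on the entry criteria to control hepatotoxicity, so the entry rule needs to work.

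**Working it through.** The plan states no figure to reproduce. The check is one of logic, followed by a comparison with the stopping rules.

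**Step 1: criterion 9 as a truth table.** Let A = ALT >2.5×ULN, B = bilirubin >1.5×ULN, and D = fractionated with direct bilirubin <35%. The exception applies when B holds, A does not, and D holds. In the table, 1 means yes or excluded.

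| A | B | D | A and B | A and B, with exception | A or B | A or B, with exception |
|---|---|---|---|---|---|---|
| 0 | 0 | 0 | 0 | 0 | 0 | 0 |
| 0 | 0 | 1 | 0 | 0 | 0 | 0 |
| 0 | 1 | 0 | 0 | 0 | 1 | 1 |
| 0 | 1 | 1 | 0 | 0 | 1 | 0 |
| 1 | 0 | 0 | 0 | 0 | 1 | 1 |
| 1 | 0 | 1 | 0 | 0 | 1 | 1 |
| 1 | 1 | 0 | 1 | 1 | 1 | 1 |
| 1 | 1 | 1 | 1 | 1 | 1 | 1 |
| **Total** | | | **2** | **2** | **6** | **5** |

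- With *and*: 2 of 8 excluded, and the exception changes 2 − 2 = 0.
- With *or*: 6 of 8 covered, and the exception readmits 6 − 5 = 1. Both isolated-ALT rows are excluded.

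D matters only when bilirubin alone is raised, so three pairs of rows merge and 8 − 3 = 5 distinct clinical states remain. On that count, *and* excludes 1 of 5 and the exception changes 0. *Or* covers 4, readmits 1 and leaves 3 excluded. The conclusion is the same.

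**Step 2: any other numeric ALT limit at entry.** The inclusion criteria in 4.2 have none. Among the other exclusion criteria in 4.3, criterion 10 is a clinical definition without an ALT value and criterion 11 rests on investigator opinion. Neither amendment listed in Protocol Appendix 6 touches criterion 9, and the SAP does not correct it.

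**Step 3: isolated ALT at entry against the 6.4.9 stopping criteria, if the value is unchanged on treatment.**

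| Isolated ALT at entry | Position under 6.4.9 |
|---|---|
| ≥8×ULN | Meets criterion 2 at once |
| ≥5 to <8×ULN | Meets criterion 3 if it persists for 2 weeks or more; criterion 5 if weekly monitoring is not possible |
| ≥3 to <5×ULN | Meets criterion 4 only with symptoms believed to be hepatitis or hypersensitivity; criterion 1 only with INR >1.5 or the required bilirubin rise |
| >2.5 to <3×ULN | Meets none |

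The 3×ULN floor of the stopping criteria lies just above the 2.5×ULN entry limit, which fits an entry limit meant to stand alone.

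**Step 4: effect on the primary analysis.** A subject taken off drug is asked to attend the remaining MMTT visits (Protocol 4.4), and the primary analysis in SAP 7.1.1.1 uses all on-study data. The endpoint is not lost; the exposure is.

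**The case against.** The strongest reply is that this is a drafting slip with clinical backstops. A reader who gives the whole criterion effect would infer *or*, and the instructions that sites received in the Study Procedures Manual are not visible here. An investigator who sees a screening ALT of 8×ULN is unlikely to enrol the subject, and criterion 11 then requires exclusion if the abnormality is judged an added risk. Hepatitis screening and the 6.4.9 stopping rules give further cover. For asymptomatic ALT between 2.5 and 5×ULN, where discretion matters most, the stopping rules rarely bite. The combination counts are unweighted and say nothing about frequency. SAP 11.6.1 records poor enrolment, and *or* would exclude some subjects with stable hepatitis B or C.

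Much of this stands. The extreme case is unlikely, the counts describe logic and not risk, and no exposure can be quantified. It does not remove the defect. Under a no-deviations clause sites should not have to infer intent, criterion 11 has no threshold and can be applied differently between sites, and criterion 10 accepts stable hepatitis only for subjects who pass the other entry rules.

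**Conclusion.** The concern holds. On its literal wording, criterion 9 makes its own exception inoperative (0 of 8 combinations changed) and leaves isolated ALT without a numeric entry limit. It can therefore admit subjects who already meet a stopping criterion.

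This rests on reading the criterion as written, and on ALT staying at its screening level for the stopping rules to apply. That *or* was intended is an inference from the parenthesis. The rate of isolated ALT above 2.5×ULN in subjects aged 18 to 30 is not given, and few may be affected. There is no direct effect on the sample size or the primary analysis. The wording should be corrected for subject safety, consistent screening and avoidance of early drug withdrawal.

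**What to change.** In criterion 9, change *and* to *or* between the two limits, so that it reads ALT >2.5×ULN or bilirubin >1.5×ULN, and leave the parenthesis on isolated bilirubin as it stands.

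The cost is one word in a protocol amendment. No new test is needed: ALT, total bilirubin and direct bilirubin are already in the screening chemistry panel (Protocol Table 3, note 17). A few more subjects may fail screening, possibly including some with stable hepatitis B or C; the documents give no figure for this. Amendment 01 already corrected a wording error in criterion 11, so a change of this kind has precedent in the study.
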